1.2 Purpose

Study CKJX839C12301 (ORION-16) is a pivotal phase III study designed to evaluate safety, tolerability, and efficacy of inclisiran in adolescents (aged 12 to <18 years) with HeFH and LDL-C >130 mg/dL (3.4 mmol/L). The use of inclisiran (as an adjunct to stable, optimal background lipid-lowering therapy) for the treatment of HeFH in adolescent patients who require additional lipid-lowering will be investigated in order to obtain needed pediatric information on inclisiran. The follow-up period (Part 2/Year 2) serves to collect longer-term data on inclisiran and also allows access of study participants to a potentially effective treatment.

2 Objectives and endpoints

Table 2-1 Objectives and related endpoints

Objective(s)	Endpoint(s)	
Primary objective(s)	Endpoint(s) for primary objective(s)	
• The primary objective is to demonstrate superiority of inclisiran compared to placebo in reducing LDL-C [percent change] at Day 330 (Year 1) in adolescents (aged 12 to <18 years) with HeFH and elevated LDL-C	 Percentage change in LDL-C from baseline to Day 330 (Year 1) See Section 2.1 for primary estimand 	
Secondary objective(s)	Endpoint(s) for secondary objective(s)	
Demonstrate superiority of inclisiran compared to placebo in reducing LDL-C [time-adjusted percent change] over Year 1	• Time-adjusted percent change in LDL-C from baseline after Day 90 and up to Day 330 (Year 1)	
Demonstrate superiority of inclisiran compared to placebo in reducing LDL-C [absolute change] at Day 330 (Year 1)	 Absolute change in LDL-C from baseline to Day 330 (Year 1) 	

Objective(s)	Endpoint(s)		
Demonstrate superiority of inclisiran compared to placebo in reducing Apo B, lipoprotein (a) [Lp(a)], non-high density lipoprotein cholesterol (non-HDL-C), and total cholesterol [percent change] at Day 330 (Year 1)	Percent change in Apo B, Lp(a), non-HDL-C, and total cholesterol from baseline to Day 330 (Year 1)		
• Evaluate the effect of inclisiran, compared to placebo (for Year 1) and long-term (up to Day 720), on lowering LDL-C, other lipoprotein and lipid parameters, and PCSK9 over time	 Percent change and absolute change in LDL-C, Apo B, Lp(a), non-HDL-C, total cholesterol, triglycerides, high density lipoprotein cholesterol (HDL-C), very low density lipoprotein cholesterol (VLDL-C), apolipoprotein A1 (Apo A1) and PCSK9 from baseline to each assessment time up to Day 720 (Year 2) 		
• Evaluate the safety and tolerability profile of inclisiran, compared to placebo (for Year 1) and long-term (up to Day 720), in adolescents (aged 12 to <18 years) with HeFH	 Incidence, severity and relationship to study drug of treatment-emergent adverse events (AEs) and serious adverse events (SAEs); vital signs; laboratory parameters; anti-drug antibodies (ADA) measurement; growth (height, weight, body mass index (BMI)); pubertal development (steroid hormones and Tanner staging) 		

2.1 Primary estimands

The primary clinical question of interest is: What is the effect of the test treatment versus placebo on change in LDL-C after 330 days of treatment in adolescents with HeFH who are on stable, optimal standard of care (SoC) lipid-lowering therapy, regardless of treatment discontinuation for any reason and regardless of unforeseen change in the concomitant lipid-lowering therapy.

The justification for the primary estimand is that it will capture both the effect of the study drug and the effect of changes in additional medication(s) used for HeFH, if they occur, as would be the case in clinical practice.

The primary estimand is described by the following attributes:

- 1. Population: Adolescents with the HeFH condition of interest and elevated LDL-C on stable optimal SoC lipid-lowering therapy. Further details about the population are provided in Section 5.
- 2. Endpoint: Percentage change in LDL-C from baseline to Day 330 (Year 1).
- 3. Treatment of interest: The randomized treatment (the investigational treatment inclisiran or the control treatment placebo) as add-on to optimal SoC lipid-lowering therapy for HeFH. The type and dose of the concomitant lipid-lowering therapy for HeFH must remain stable during Part 1 (Year 1) of the study. Further details about the investigational treatment and control treatment are provided in Section 6.

The summary measure: difference between treatments in least squares mean percentage change at Day 330.

2.2 Secondary estimands

Secondary estimands corresponding to key secondary efficacy endpoints are defined similarly to the primary estimand. These endpoints, and the corresponding summary measures, are listed below. Population, treatment of interest, endpoints, and intercurrent events are defined similarly as for the primary estimand.

- Endpoint: time-adjusted percent change in LDL-C from baseline after Day 90 and up to Day 330 (Year 1). Summary measure: difference between treatment groups in least squares mean time-adjusted percent change in LDL-C from baseline after Day 90 and up to Day 330 (Year 1).
- Endpoint: absolute change in LDL-C from baseline to Day 330 (Year 1). Summary measure: difference between treatment groups in least squares mean absolute change in LDL-C from baseline to Day 330 (Year 1).
- Endpoint: percent change in Apo B from baseline to Day 330 (Year 1). Summary measure: difference between treatment groups in least squares mean percent change in Apo B from baseline to Day 330 (Year 1).
- Endpoint: percent change in Lp(a) from baseline to Day 330 (Year 1). Summary measure: difference between treatment groups in least squares mean percent change in Lp(a) from baseline to Day 330 (Year 1).
- Endpoint: percent change in non-HDL-C from baseline to Day 330 (Year 1). Summary measure: difference between treatment groups in least squares mean percent change in non-HDL-C from baseline to Day 330 (Year 1).
- Endpoint: percent change in total cholesterol from baseline to Day 330 (Year 1). Summary measure: difference between treatment groups in least squares mean percent change in total cholesterol from baseline to Day 330 (Year 1).

3 Study design

This study is a two-part (double-blind, placebo-controlled / open-label) multicenter study in adolescents (aged 12 to <18 years) with HeFH and elevated LDL-C (>130 mg/dL / 3.4 mmol/L) on stable, individualized, optimal SoC background lipid-lowering therapy (including maximally tolerated statin treatment).

The overall study duration is 748 days (excluding a safety follow-up call 30 days after the end of study (EOS) visit).

Following an approximately 4 weeks screening/run-in period, the study has two sequential parts (Figure 3-1).

- **Part 1 (Year 1):** 12 months double-blind, parallel group period in which participants will be randomized to receive either inclisiran sodium 300 mg (equivalent to 284 mg inclisiran^{*}) s.c. or placebo (given at Days 1, 90 and 270).
- **Part 2 (Year 2):** 12 months single arm, open-label follow-up period with all participants receiving inclisiran sodium 300 mg (equivalent to 284 mg inclisiran^{*}) s.c. Participants randomized to placebo in Part 1 will receive inclisiran starting on Day 360 ("Switch" Day 360). Participants randomized to inclisiran in Part 1 will receive placebo on Day 360. This dose of inclisiran/placebo on Day 360 will remain blinded in order to maintain the blind for Part 1 of the study. All participants will receive subsequent doses of open-label inclisiran on Days 450 and 630.
- * Inclisiran is also referred to as KJX839.

[figure not shown]
Informed consent will be obtained before initiation of any study-specific procedures (see Section 5.1 and Section 7 for details). Participants who meet the inclusion/exclusion criteria will be required to maintain their current lipid-lowering treatment unchanged for Part 1 (Year 1) of the study (including the screening/run-in period). Investigators must ensure that each participant receives individualized, optimal SoC lipid-modifying treatment [including maximally tolerated statin treatment (investigator's discretion) with or without other lipid-lowering therapy (e.g. ezetimibe)], and that this treatment was stable for \geq 30 days before screening. Maximum tolerated dose of statin is defined as the maximum dose of statin that, at the investigator's discretion, can be taken on a regular basis without AEs that would lead to a reduction in statin dose. Intolerance to statin must be documented and enrollment of statin-intolerant participants will be capped at approximately 15%.

A minimum of 102 participants (actual expected number of participants: approximately 130) who meet the inclusion/exclusion criteria will be randomized in a 2:1 ratio to receive either inclisiran sodium 300 mg s.c. or placebo on Day 1 (baseline). Randomization will be stratified by age (\geq 12 to <15 years and \geq 15 to <18 years to include a minimum of 40 participants in each of the two age strata). A second and third dose of inclisiran or placebo will be given on Day 90 and Day 270, respectively. The primary endpoint will be measured at Day 330.

Participants initially randomized to placebo will transition to inclisiran starting on Day 360 and the study will then change to an open-label, single arm follow-up period of inclisiran sodium 300 mg s.c. (Part 2). In order to maintain the blind for Part 1 of the study, on the "switch" day (Day 360), participants randomized to placebo in Part 1 will receive blinded inclisiran, while participants randomized to inclisiran in Part 1 will receive blinded placebo. All participants will receive subsequent doses of open-label inclisiran on Day 450 and Day 630.

The EOS visit will be on Day 720. In addition, a safety follow-up call will be conducted 30 days after the last study visit or 90 days after the last administration of study drug, whatever is longer.

* Primary endpoint assessed at Day 330. # "Switch Day": Participants randomized to placebo in Part 1 will start to receive inclisiran on Day 360. Participants randomized to inclisiran in Part 1 will receive placebo on Day 360 only to maintain the blind for Part 1.

Inclisiran and placebo will be administered exclusively by a health care provider at the study site. Participants will be observed in the clinic for at least 4 hours post injection on Day 1 and Day 360 (i.e. first dosing of inclisiran) and for at least 30 minutes post injection for all other dosing visits before being discharged.

Participants on a documented regimen of low density lipoprotein (LDL)-apheresis will be allowed to continue their same regimen during the study, if needed. The apheresis schedule is not allowed to change during Part 1 (Year 1) of the study (including the screening/run-in period). The apheresis schedule must also allow that an apheresis coincides with each study visit. Study drug is to be administered the same day, after completion of apheresis (the next scheduled apheresis should not occur within 72 hours after an administration of study drug). Blood samples for LDL-C (and other laboratory assessments of efficacy and safety) must be obtained immediately before the scheduled apheresis treatment at each applicable study visit (including screening and baseline (Day 1)).

4 Rationale

4.1 Rationale for study design

Part 1 of the study (Year 1) has a randomized, parallel group, placebo-controlled design to provide evidence for the efficacy, safety, and tolerability of inclisiran in adolescents with HeFH. This study design is the most appropriate trial design to answer the clinical questions of interest on the use of inclisiran in this pediatric patient population.

The open-label single-arm design for Part 2 of the study (Year 2) is appropriate to obtain additional long-term data, with a maximum number of participants exposed to the investigational drug.

A screening/run-in period of approximately 4 weeks is used to ensure the entry criteria are met (allowing test results to be received) and to ensure stabilization of individualized, optimal SoC background lipid-lowering therapy prior to randomization.

An unequal 2:1 randomization was chosen in agreement with regulatory authorities. This unequal randomization allows to maximize exposure to the active investigational drug and to enhance collection of corresponding efficacy/safety information in the pediatric study population.

4.1.1 Rationale for choice of background therapy

It is required that all participants receive individualized, optimal SoC lipid-lowering treatment for HeFH at study entry, which must remain unchanged for Part 1 (Year 1) of the study (including the screening/run-in period). Optimal SoC for adolescents with HeFH comprises maximally tolerated statin treatment with or without additional lipid-lowering treatment (e.g. ezetimibe), in accordance with international/local practice and treatment guidelines as well as regulatory authorities. No specific background medication is required during the conduct of the study; any statin and other lipid-lowering therapies approved for use in this population may be used (unless specifically prohibited per protocol; see Section 5.2 and Section 6.2.2 for details).

4.2 Rationale for dose/regimen and duration of treatment

The established dose regimen for inclisiran for adults is 300 mg s.c. on Day 1, Day 90 and every 6 months thereafter. Based on nonclinical and clinical data, including phase I, II and III clinical studies as well as pharmacodynamic (PD) modeling in adult participants, the same dose and dose regimen will also be used in the present study in adolescents.

In adult participants, maximum reductions in LDL-C and PCSK9 levels with inclisiran were achieved with single s.c. doses of 300 mg inclisiran sodium, with no additional meaningful benefit observed at higher doses. Three large pivotal phase III studies in adult participants with ASCVD, ASCVD risk equivalents, and/or HeFH demonstrated that the dose regimen used in the present study (300 mg inclisiran sodium s.c. on Day 1, Day 90 and every 6 months thereafter) resulted in placebo-adjusted percentage reductions in LDL-C from baseline at Day 510 of 48% to 52%, with time-adjusted average reductions of 44% to 54% sustained over 18 months. This dose and regimen also showed good tolerability of inclisiran, with a safety profile similar to placebo, except for a higher incidence of AEs at the injection site with inclisiran. No patient populations were identified that required an inclisiran dose adjustment. Doses up to 900 mg (3-fold therapeutic dose) were studied which was safe and well tolerated in healthy adult subjects.

Adult data has shown that the plasma PK of inclisiran does not predict PD effects. Inclisiran is rapidly cleared from plasma in 24 to 48 hours depending on the dose level, yet because of its site and mechanism of action, its LDL-C lowering effect is measurable for more than 6 months even after a single dose, the basis of the 6-monthly dosing interval. Inclisiran is delivered to hepatocytes due to its conjugated structure with GalNAc and stored intracellularly in RISC complexes, where target protein suppression occurs for months, resulting in the disconnect

between plasma PK and PD effects. In view of this time dissociation between PK and PD data, a plasma concentration vs. PD effect relationship cannot be established. From phase I study data, only a weak relationship was observed between inclisiran C_{max} and minimum LDL-C levels, due to the indirect processes involved between s.c. administration of inclisiran and reduction of LDL-C in the bloodstream. Additionally, after multiple administrations in the phase I study, inclisiran plasma exposure ratios were close to one, indicating no PK accumulation. A modelling and simulation analysis based on phase II study (ORION-1) data in adults suggest that the PD effect of inclisiran neither strengthens nor attenuates over time after repeated administrations up to 2 years of treatment.

In general, dosing and PK in adolescents are similar to those in adults (Momper et al 2013). Pharmacokinetics of inclisiran is expected to be similar in adolescents and adults as inclisiran is metabolized by exonuclease and endonuclease activity, with urinary excretion contributing to plasma elimination. Hence, the 300 mg dose, which has been shown to be efficacious, safe and well tolerated in adult phase III studies, as mentioned above, has been chosen as the dose for this study.

The rationale for the approximately 1 year duration of the placebo-controlled Part 1 of the study is that it allows a reasonable number of 3 injections per participant (given the twice yearly dosing regimen) and is supported by the treatment effect observed in the phase III clinical trials (up to 18 months). The duration is also suitable to assess the longer-term efficacy as well as safety and tolerability, including safety areas of special interest. The additional approximately 1-year duration of the uncontrolled Part 2 of the study is suitable to collect meaningful additional long-term data on inclisiran.

4.3 Rationale for choice of control drugs (comparator/placebo)

Part 1 of the study (which includes assessment of the primary (Efficacy) endpoint) is placebocontrolled, which is a standard design in drug development to assess efficacy and safety and ensures that differences in outcome will be a reliable/realistic measure of the treatment effect of inclisiran. The use of placebo as a comparator is justified since all enrolled participants will be treated with individualized, optimal SoC (including maximum tolerated statin \pm other lipidlowering treatment, e.g. ezetimibe) prior to the addition of study treatment.

Part 2 (1 year Safety follow-up) does not have a comparator arm; all patients will receive inclisiran, which represents a common and appropriate design to enable the collection of additional long-term safety data for the investigational drug for a maximum number of participants.

4.4 Purpose and timing of interim analyses/design adaptations

An independent Data Monitoring Committee (DMC) will review safety data regularly during the study. A recommendation may be taken to stop or amend the study at any of these reviews. Further details are provided in Section 10.2.4 and Section 12.7.

4.5 Risks and benefits

It is widely recognized that LDL-C plays a major role in the initiation and progression of ASCVD, including in HeFH, and accumulated exposure of elevated LDL-C is causally related to the development of ASCVD. As the degree and duration of exposure to elevated LDL-C levels increases the atherosclerotic burden, early treatment of HeFH is vital. Published expert guidelines recommend a LDL-C target of \leq 130 mg/dL in children/adolescents. Current treatment options to achieve these targets are still limited for children with FH and the well-known limitations of contemporary therapies are particularly relevant among pediatric patients with FH.

In adult studies in participants with ASCVD, ASCVD risk equivalents, and/or HeFH, inclisiran given on Day 1, Day 90 and every 6 month thereafter lowered LDL-C by \sim 50% versus placebo in participants on maximally tolerated statin therapy \pm other lipid-lowering therapies. The effect was persistent over time and reversible on stopping inclisiran.

In non-clinical toxicity studies, inclisiran was not carcinogenic or genotoxic, there was no effect on paternal performance, spermatogenesis, estrous cycle, and uterine or ovarian parameters and inclisiran did not show evidence of embryolethality, fetotoxicity, or teratogenicity. In addition, there were no effects of inclisiran on the development of the F1 generation, including survival, growth, physical and reflexological development, behavior, and reproductive performance. The safety profile of inclisiran in clinical studies was generally comparable to placebo. The only Adverse drug reaction (ADR) identified in clinical studies was a higher incidence of TEAEs at the injection site with inclisiran (preferred terms of injection site erythema, injection site hypersensitivity, injection site pruritus, injection site rash, and injection site reaction). However, all TEAEs at the injection site were localized, were predominantly mild or occasionally moderate, transient, and resolved without sequelae. The impact of this side effect is further mitigated by the infrequent dosing regimen of inclisiran.

In general, the risk of participants in this trial may be minimized by compliance with the eligibility criteria and study procedures, close clinical monitoring of safety parameters, as well as periodic review of the safety data by an independent DMC. Participants will also be observed in the clinic for at least 4 hours post injection on Day 1 and Day 360 (i.e. first dosing of inclisiran) and for at least 30 minutes post injection for all other dosing visits before being discharged.

Women of child bearing potential must be informed that taking the study treatment may involve unknown risks to the fetus if pregnancy were to occur during the study, and agree that in order to participate in the study they must adhere to the contraception requirements outlined in the exclusion criteria. If there is any question that the participant will not reliably comply, they should not be entered or continue in the study.

The benefit a participant might have by participating in the study is the close monitoring of their condition and close adherence to SoC lipid-lowering treatment.

5 Study Population

The study population consists of adolescents (12 to <18 years) with a genetic and/or clinical diagnosis of HeFH and LDL-C >130 mg/dL (3.4 mmol/L) on optimal SoC lipid-lowering therapy.

A minimum of 102 participants (actual expected number of participants: approximately 130) meeting the eligibility criteria will be randomized.

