6.1.4 Treatment duration

The expected duration of the participant's involvement in the study will be approximately 748 days, which includes a screening/run-in period (28 days) and subsequent treatment with study drug (1 year double-blind, placebo-controlled followed by 1 year open-label follow-up), with the EOS visit on Day 720 (Year 2). In addition, a safety follow-up call will be conducted 30 days after the last study visit or 90 days after the last administration of study drug, whatever is longer.

Participants may be discontinued from treatment earlier due to safety reasons and/or at the discretion of the investigator or the participant's parent(s)/legal representative(s) / participant (if applicable). They will continue to be followed up in the study unless informed consent is withdrawn (Section 9.1.1 and Section 9.1.2).

Participants who complete participation in this trial and continue to derive clinical benefit from the treatment based on the investigator's evaluation may receive post-trial access (see Section 9.2).

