Women of child bearing potential and her parent(s)/legal representative(s) must be informed that taking the study treatment may involve unknown risks to the fetus if pregnancy were to occur during the study and agree that in order to participate in the study they must adhere to the contraception requirements.

A copy of the approved version of all consent/assent forms must be provided to Novartis after IRB/IEC approval.

8 Visit schedule and assessments

The Assessment Schedule (Table 8-1) lists all of the assessments when they are performed. All data obtained from these assessments must be supported in the participant's source documentation.

Participants should be seen for all visits/assessments as outlined in the Assessment Schedule or as close to the designated day/time as possible. Missed or rescheduled visits should not lead to automatic discontinuation.

Participants who prematurely and permanently discontinue from study treatment will continue to be followed up in the study according to the Assessment Schedule unless informed consent is withdrawn.

Participants who prematurely discontinue the study for any reason [e.g. if a participant's parent(s)/legal representative(s) / a participant (if applicable) decide to prematurely and permanently discontinue the participant from study treatment and decline further follow-up visits] should be scheduled for an EOS visit as soon as possible. At this final visit, AEs and concomitant medications should be recorded in the corresponding eCRFs.

Participants will have to comply with the following restrictions:

- Participants should have fasted for at least 8 hours for all visits for fasting lipids/lipoproteins/PCSK9 and glucose blood samples (if the participant has not fasted, the collection of laboratory evaluations must be rescheduled)
- Participants must refrain from unaccustomed strenuous physical exercise for 48 hours before the screening and any study visit until the follow-up has been completed
- Blood donation will not be allowed at any time during the study

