8.4.3 Pregnancy

Females of child-bearing potential are defined as all females physiologically capable of becoming pregnant. This includes female adolescent participants who are menarchal or who become menarchal during the study.

Serum/urine pregnancy tests will be performed for all female adolescents of child-bearing potential according to the Assessment Schedule (Table 8-1). A positive urine pregnancy test should be confirmed with a serum pregnancy test. Additional pregnancy tests may be performed at the investigator's discretion during the study and/or if requested by local requirements.

Participants becoming pregnant must be discontinued from study drug. However, a participant may choose to remain in the study should she become pregnant, and be followed according to the protocol-defined study visits.

All menarchal adolescents and their parent(s)/legal representative(s) should be informed about the potential risks of pregnancy and the need to prevent pregnancy during the study.

It is important to be sensitive in introducing this issue, as understanding and comprehension of puberty, sexual activity, pregnancy and contraception is influenced by age as well as, factors such as precocity, socio(educational) economic and familial background. These discussions with the participant and her parent(s)/legal representative(s) are therefore best performed by investigators familiar with the adolescent participant and her family and should be guided by requirements of the local regulatory authorities. These discussions should take into account the socio-economic, cultural factors and religious beliefs of the adolescent participant and her family. The investigator should also discuss the management of the pregnancy test results with the participant and her parent(s)/legal representative(s). The privacy of the participant should be considered in accordance with the local law and ethics.

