9.1 Discontinuation and completion

9.1.1 Study treatment discontinuation and study discontinuation

Discontinuation of study treatment for a participant occurs when study treatment is stopped earlier than the protocol planned duration, and can be initiated by either the participant's parent(s)/legal representative(s) / participant (if applicable) or the investigator.

The investigator must discontinue study treatment for a given participant if, he/she believes that continuation would negatively impact the participant's well-being. After study treatment discontinuation, participants should remain in the study and complete other study visit procedures as per the Assessment Schedule, unless consent is withdrawn (Section 9.1.2), preferably in writing.

Study treatment must be discontinued under the following circumstances:

- Participant's parent(s)/legal representative(s) / participant (if applicable) decision
- Pregnancy
- Use of prohibited treatment as per details in the prohibited treatment section (Table 6-2)
- Following emergency unblinding
- Any situation in which study participation might result in a safety risk to the participant
- Severe and persistent (>14 days despite appropriate treatment) reactions at the injection site and any confirmed anaphylactic reactions
- Unexplained increases in transaminases (ALT or AST) or total bilirubin as follows:
 - ALT or AST >5x ULN
 - ALT or AST >3x ULN for more than 2 weeks
 - ALT or AST >3x ULN and (total bilirubin >2x ULN or INR >1.5)
 - ALT or AST >3x ULN with the appearance of fatigue, nausea, vomiting, right upper quadrant pain or tenderness, fever, rash, and/or eosinophilia (>5%)
 - The investigator should evaluate to see if other causes for the laboratory abnormalities are immediately apparent, such as obstructive gall bladder or bile duct disease, viral or alcoholic hepatitis, malignancy involving the liver, congestive hepatopathy, other hepatotoxins or heritable disorders.
- Unexplained C(P)K values >5x ULN confirmed by repeat test when the C(P)K elevation is associated with muscle pain, muscle tenderness and/or muscle weakness, or new onset renal dysfunction
- Any other laboratory abnormalities that, in the judgment of the investigator, prevents the participant from continuing study treatment

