In addition, adolescent females who gain child-bearing potential during the study and are unwilling to comply with the requirements for contraception as outlined in Section 5.2 will be excluded from receiving further study drug.

If discontinuation of study treatment occurs, the investigator should make a reasonable effort to understand the primary reason for the participant's premature discontinuation of study treatment and record this information.

Study treatment may be restarted at the discretion of the investigator, if the reason for discontinuation has resolved. Every effort should be made to restart study treatment, if deemed appropriate by the investigator. Study treatment is **not** allowed to be re-started following initiation of prohibited medication that requires study drug discontinuation (Table 6-2).

Participants who discontinue study treatment or for whom the participant's parent(s)/legal representative(s) / participant (if applicable) decide that they do not to wish the participant to participate in the study further, should NOT be considered withdrawn from the study UNLESS informed consent was withdrawn (see Withdrawal of informed consent, Section 9.1.2). Where **possible, they should return for the assessments indicated** in the Assessment Schedule. If they fail to return for these assessments for unknown reasons, every effort (e.g. telephone, e-mail, letter) should be made to contact the participant's parent(s)/legal representative(s) / participant / pre-designated contact as specified in the lost to follow-up section. This contact should preferably be done according to the study visit schedule.

If the participant cannot or is unwilling to attend any visit(s), the site staff should maintain regular telephone contact with the participant, the participant's parent(s)/legal representative(s) or with another pre-designated person. This telephone contact should preferably be done according to the study visit schedule.

After study treatment discontinuation, at a minimum, in abbreviated visits, the following data should be collected at clinic visits and/or via telephone/email contact:

- New / concomitant treatments
- AEs/SAEs

Where possible, all clinic visit assessments should be performed according to Table 8-1.

The investigator must also contact the IRT to register the participant's discontinuation from study treatment.

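### Protocol Section 4.5 removes a participant from the study when contraception is in doubt, while the follow-up rules stop study drug only; a site that follows 4.5 literally can lose an obtainable Day 330 LDL-C

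*Protocol*

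**What the plan says.** Protocol Section 4.5 (Risks and benefits) first warns of unknown fetal risk and requires adherence to the contraception rules. It then instructs the site: "If there is any question that the participant will not reliably comply, they should not be entered or continue in the study".

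Other sections give a different rule for a participant who has already been randomized:

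- Section 6.1.4, on participants taken off treatment early: "They will continue to be followed up in the study unless informed consent is withdrawn".
- Section 8, on permanent discontinuation of study treatment: such participants "will continue to be followed up in the study according to the Assessment Schedule unless informed consent is withdrawn".
- Section 9.1.1, general rule: "After study treatment discontinuation, participants should remain in the study and complete other study visit procedures". It adds that they "should NOT be considered withdrawn from the study UNLESS informed consent was withdrawn".
- Section 9.1.1, on girls who gain child-bearing potential during the study and will not use contraception: they "will be excluded from receiving further study drug".
- Section 8.4.3: study drug stops on pregnancy, but "a participant may choose to remain in the study should she become pregnant".

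The primary estimand in Section 2.1 asks for the effect "regardless of treatment discontinuation for any reason". SAP Section 2.5.1 labels this a treatment policy strategy.

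**The concern.** Read as written, Section 4.5 ends a girl's participation on mere doubt about contraception, while an actual pregnancy does not. The glossary distinguishes stopping study treatment from leaving the study, and after leaving, no further assessments are planned. A site that follows 4.5 therefore stops collecting LDL-C in someone who is still willing to attend.

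Off-treatment LDL-C is exactly what a treatment policy estimand needs. If the Day 330 value is lost, it is replaced by a model-based value, and in the inclisiran arm that value is built from placebo data. The point at stake is the completeness of observed primary data and a small attenuation of the estimate, not the superiority conclusion.

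**Working it through.** **1. Is the conflict real?** Section 4.5 contains two instructions. Not entering a doubtful participant agrees with exclusion criterion 3 in Section 5.2. Not continuing her in the study conflicts with the general follow-up rule in Sections 6.1.4, 8 and 9.1.1. The contraception sentence in 9.1.1 is narrower, covering only girls who gain child-bearing potential on study, and 8.4.3 has a different trigger (pregnancy). For other participants the conflict is thus with the general rule. Section 5.2 requires contraception only while study treatment is being dosed, so once drug is stopped no contraception reason for leaving remains.

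**2. When would Day 330 be missing?** SAP Table 2-1 maps an early-exit visit to the next scheduled visit. If the last attended visit is Day 270, the exit visit counts as Day 330, and the end-of-study column of protocol Table 8-1 includes fasting LDL-C. If the last attended visit is earlier, the exit visit maps to Day 270 or before and Day 330 is missing. It is also missing if no exit LDL-C is obtained.

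**3. What replaces it?** Under SAP Section 5.7.1, an inclisiran participant who leaves without data after Day 330 does not qualify for step 3 (missing at random). She falls under step 4, which imputes Day 330 from placebo data using baseline value and age group. A placebo participant is imputed as missing at random within her own arm.

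**4. Size per affected inclisiran participant.** Inputs:

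- Effect E = 48 to 52 percentage points (adult phase III range at Day 510, protocol Section 4.2). The design effect for this trial is redacted.
- n on inclisiran = 141 × 2/3 = 94 (141 enrolled, SAP Section 1.1, with exact 2:1 allocation assumed).
- r = share of the effect that would remain at Day 330 after drug is stopped. The documents do not give it, so the full range 0 to 1 is used.

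If observed, her Day 330 difference from placebo would be r × E on average. The imputed difference is about 0. The shift of the arm mean towards no effect is therefore E × r / n.

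| r | E = 48 | E = 52 |
|---|---|---|
| 0 | 0 | 0 |
| 0.5 | 48 × 0.5 / 94 = 0.26 | 52 × 0.5 / 94 = 0.28 |
| 1 | 48 / 94 = 0.51 | 52 / 94 = 0.55 |

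As a share of the effect, the maximum is 1/94 = 1.06%. At the protocol minimum of 102 participants (68 on inclisiran) the maximum would be 48/68 = 0.71 to 52/68 = 0.76 points.

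**5. How large is r likely to be?** A participant who exits before Day 270 had her last dose on Day 90 or Day 1, that is 330 − 90 = 240 or 330 − 1 = 329 days before Day 330. Section 4.2 says the effect of one dose is measurable for more than 6 months, and Section 4.5 says it is reversible. Some residual effect is plausible, but r may be well below 1.

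**6. Effect on power, for scale only.** Take a 48-point effect, an assumed common SD of 20 to 50 (the planned SDs are redacted), one-sided alpha 0.025 and 102 participants. Power is at least 99.5% with no loss, and at least 98.8% with five inclisiran participants lost and imputed at r = 1.

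**The case against.** The strongest reply is that Section 4.5 is risk-benefit narrative and Section 9.1.1 is the section a site works from. Section 9.1.1 lists safety risk as a ground for stopping treatment and says emphatically that participants are not withdrawn unless consent is. The sentence in 4.5 follows one about taking study treatment, so it could be read loosely as continuing on drug. The harm also needs a chain: doubt arises after randomization, the site follows 4.5 over 9.1.1, and the participant exits before Day 270 or without an exit LDL-C. The resulting bias is small and runs against inclisiran.

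Most of this stands, and it limits the point to a minor one. It does not remove it. Section 4.5 is a direct instruction, specific to doubt about contraception, with no cross-reference to 9.1.1, and nothing in the protocol says which section prevails. Because the glossary separates stopping treatment from leaving the study, the loose reading is not secure.

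A further objection is timing: the SAP reports 141 enrolled and analyses made after the Part 1 lock, so an edit now cannot recover Part 1 values. That is correct.

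**Conclusion.** The concern holds. The instruction in Section 4.5 not to continue such a participant in the study is wrong as written, because following it gives a worse result than the follow-up rule in the rest of the protocol. The loss is conditional. It arises only if a site acts on 4.5 and the participant leaves before attending Day 270 or without an exit LDL-C.

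For each affected inclisiran participant the estimate moves towards zero by 0 to 0.55 points, at most about 1.1% of the effect. This rests on the adult effect range, 94 participants on inclisiran, and placebo-level imputation. The residual share r is an assumption, and the number of affected participants is not in the documents. Superiority is not threatened. This is a recommended correction, not a critical one.

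**What to change.** Replace the sentence in Section 4.5 with: *If there is doubt about compliance, the participant should not be entered or receive further study drug; visits and LDL-C sampling continue per Section 9.1.1 unless consent is withdrawn.* The decision on study drug is unchanged and no assessment is added, since the visits and samples are already in Table 8-1. The edit is one sentence, but under Section 14.1 it needs a written amendment with the usual approvals.

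Because Part 1 is locked, also review the discontinuation reasons summarised under SAP Section 2.3.1 for participants removed on contraception grounds. Report how many there were, by arm, and how many of them lack an observed Day 330 LDL-C.
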